### 5.5.2 Procedures for discontinuation

Subjects who discontinue should always be asked about the reason(s) for their discontinuation and the presence of any safety issues. If possible, they should be seen and assessed by an Investigator. The Termination section in the CRF should be completed. Safety events should be followed up. Any study specific material provided to the subject should be collected.

The reimbursement of the treatment will be reduced as described in the CSA, as applicable.

Removed Investigational Products will be returned to Dentsply Sirona Implants for further investigation.

After discontinuation appropriate further treatment will be initiated according to the Investigator's judgment and according to local medical practice.

# 5.5.3 Procedure for handling enrolled subjects that fail to fulfill inclusion/ exclusion criteria

If a subject has been enrolled, but no study-related surgical procedures were performed (withdrawal of consent, not meeting all pre-surgical criteria etc.) the Investigator must document this in the subject records. The subject should be discontinued and no follow-up is necessary from a study perspective.

If a subject has been enrolled and study-related surgery started, but for any reason no Investigational Product (IP) could be inserted (e.g. not enough bone according to inclusion/exclusion criteria), the Investigator must document this in the subject records. The subject should be discontinued and no follow-up is necessary from a study perspective. However the subject should be treated according to standard practice.

If a subject has been enrolled and received the IP, although the inclusion/ exclusion criteria are violated, the subject will continue in the study, but will not be part of the Per Protocol (PP) analysis.

If a subject will not receive the permanent restoration within 6 months after implant placement, the subject will discontinue the study (not eligible according to Inclusion criteria no. 17) and no follow-up is necessary from a study perspective.

• If a subject lose the study implant (implant failure) before the permanent restoration is in place, the subject will discontinue the study and no follow-up is necessary from a study perspective.

# 6 Study methodology

# 6.1 Prior and concomitant treatment(s)

Systemic corticosteroids, iv bisphosphonates or any other medication that could compromise post-operative healing and/or osseointegration should be avoided during the study period.

Subjects requiring sedation or general anesthesia before the operation will receive this in accordance with the clinic's normal routine.

Antibiotic prophylaxis will be given according to the clinic's normal routine.

After surgery, mouth rinsing with chlorhexidine 0.10 or 0.12 %, twice daily for 10 days will be prescribed. If necessary, as deemed by the investigator, this period can be prolonged.

Other medication, which is considered necessary for the subject's safety and well-being, may be given at the discretion of the investigator(s). Details of all medication (including analgesics, sedation and antibiotics) will be recorded in the eCRF on the medication page.

For prohibited medication, see 5.3.3.2 Exclusion criteria.

## 6.2 Demographics and other baseline characteristics

- Date of birth
- Gender
- Relevant medical and surgical history

- Concurrent medication
- Oral examination
- Status of dentition
- Smoking status
- Implant, abutment and crown details
- Bone quantity and quality
- Surgical approach (one- or two-stage surgery, healed site, extraction socket)
- Implant stability
- Loading regimen
- Temporary restoration
- Impression details
- Permanent restoration

### 6.3 Assessments of outcome variables

One implant per subject will be placed within the study. Implant and subject level will be equivalent, and from hereon it will be stated implant level.

### 6.3.1 Primary outcome variable

### 6.3.1.1 Prosthetic survival 1 year after permanent restoration

Prosthetic survival will be determined by evaluating presence of original permanent restoration, remained retention between abutment and final cap, and occurrence of fracture/loss of abutment

### 6.3.1.2 Assessment of primary outcome variable

Prosthetic survival will be categorized as No/Yes.

It will be categorized as 'Yes' if all of the following criteria is fulfilled:

- permanent restoration is remaining in situ
- no loss of conometric retention between abutment and final cap
- no fracture of abutment
- no loss of abutment

It will be categorized as 'No' if any of the following is fulfilled:

- permanent restoration not in situ
- loss of conometric retention between abutment and final cap
- fracture of abutment
- loss of abutment

### 6.3.2 Secondary outcome variables

#### 6.3.2.1 Prosthetic survival 3 and up 5 year after permanent restoration

Prosthetic survival will be determined by evaluating presence of original permanent restoration, remained retention between abutment and final cap, and occurrence of fracture/loss of abutment.

6.3.2.1.1 Assessment of prosthetic survival 3 and 5 year after permanent restoration Prosthetic survival will be categorized as No/Yes (see Assessment of primary outcome variable).

#### 6.3.2.2 Implant survival

Implant survival rate up to five years after permanent restoration (number of implants in situ). Any implant that is removed or lost after permanent restoration will be considered an implant loss, whatever the reason for removal.

#### 6.3.2.2.1 Assessment of Implant survival

Implant survival will be categorized as success (No/Yes)

Number of remaining implants counted clinically and radiographically, i.e. 'Yes' or 'No' for each implant where 'Yes' means that the implant is still remaining in situ and 'No' means that the implant is not in situ. Implant survival rate will be analyzed on an implant level, i.e. proportion survived implants.

#### 6.3.2.3 Marginal Bone Levels

Marginal bone levels will be determined from the radiographs, expressed as the distance from the implant reference point to the most coronal bone-to-implant contact on the mesial and distal side of the implant.

#### 6.3.2.3.1 Assessment of marginal bone levels

Intraoral radiographs will be used to assess marginal bone levels. To ensure reproducibility between the examinations, radiographs will be taken with parallel technique using film holders, whenever possible. The threaded profile of the marginal portion of the implant, both mesially and distally, must be clearly visible. If pathology around the implant is suspected, supplementary periapical x-rays should be taken. Peri-implant radiolucency will be recorded as present or absent. Double film and/or digital radiographs may be used and a hard copy or electronic copy of the image will always be retained on site for future reference. Distances from a reference point on the implant to the most coronal bone-to-implant contact on the mesial and distal aspect of the implant will be recorded. All radiographs will be evaluated by a radiologist independent from the investigational group.

#### 6.3.2.4 Condition of periimplant mucosa

Condition of periimplant mucosa will be measured by assessing of Probing Pocket Depth (PPD) and Bleeding on Probing (BoP). Presence of plague will be recorded.

#### 6.3.2.4.1 Assessment of periimplant mucosa

PPD and BoP will be evaluated at four surfaces around the implant (mesial, distal, buccal and lingual), by using a periodontal probe. PPD will be measured as the distance from the mucosal margin to the bottom of the probable pocket in mm. Bleeding will be recorded as presence or absence of bleeding when probing to the bottom of the pocket. Plaque will be recorded as presence or absence of plaque by visual inspection on four surfaces at each implant site.

For PPD mean values will be calculated for each implant. Changes over time will be analyzed. The proportion of surfaces that shows presence of bleeding when measuring probing pocket depth will be calculated and presented on an implant level for each visit. Changes over time will be analyzed.

For plaque the proportion of surfaces with presence of plaque will be calculated and presented on an implant level for each visit. Changes over time will be analyzed.

# 6.4 Safety definitions and reporting

## 6.4.1 Types of safety events

An overview of the different types of AEs can be found in 6.4.1 Types of safety events.

#### 6.4.1.1 Adverse Event (AE)

An AE is any untoward medical occurrence, unintended disease or injury, or untoward clinical signs (including abnormal laboratory findings) in subjects, users or other persons, whether or not related to the Investigational Product (IP) or the procedures involved. For users or other persons, this definition is restricted to events related to the IP.

All safety events involving subjects start as an AE, but might be further defined as ADE, SAE or SADE depending of the severity of the complication, or if judged as related to the medical device or procedure.

#### 6.4.1.2 Adverse Device Effect (ADE)

An ADE is an AE related to the use of the medical device, i.e. not only the Investigational Product (IP), but also other medical devices used in the study, e.g. implants, conometric temporization cap and other prosthetic parts.

This includes AEs resulting from insufficient or inadequate instructions for use, installation, or operation, or any malfunction of the medical device. This includes any events resulting from use error or from intentional misuse of the medical device.

#### 6.4.1.3 Serious Adverse Event (SAE)

An SAE is an AE that:

- led to death.
- led to serious deterioration in the health of the subject, that either resulted in
  - a life-threatening illness or injury, or
  - a permanent impairment of a body structure or a body function, or
  - in-patient or prolonged hospitalization (Hospital admissions and/or surgical operations that were planned before or during the study for a pre-existing condition, without serious deterioration in health, is NOT considered an SAE), or
  - medical or surgical intervention to prevent life-threatening illness or injury or permanent impairment to a body structure or a body function,
- led to foetal distress, foetal death or a congenital abnormality or birth defect.

#### 6.4.1.4 Serious Adverse Device Effect (SADE)

An SADE is an ADE that has resulted in any of the consequences characteristic of a SAE.

### 6.4.1.5 Device Deficiency (DD)

A DD is the inadequacy of a medical device with respect to its identity, quality, durability, reliability, safety or performance. This includes malfunctions, use errors, and inadequate labeling. A DD is an event associated with the product itself, not with the subject.

NB! Pay special attention to device deficiencies that might have led to an SADE if:

- suitable action had not been taken, or
- intervention had not been made, or
- circumstances had been less fortunate.

# 6.4.2 AE and ADE reporting

In clinical studies, an AE can include an untoward medical condition occurring at any time, including run-in or follow-up periods, even if the subject has not been exposed to the medical device. Subjects will be observed and asked about 'any health or oral health problems since last visit' during the study. All health/oral problems, reported by the subject, found in medical records or found at the clinic visits, must be recorded in the eCRF as an AE. Information that will be collected includes:

- Event description
- Start date
- Stop date or event continuing
- Serious yes/no
- Medical device/procedure related yes/no
- Action taken due to the event
- Clinical outcome of event

If an AE is assessed to be device/procedure related it is defined as an ADE, and must be recorded in eCRF.

If an AE/ADE results in a subject's discontinuation in the study, this should be recorded at the Study Termination page in the eCRF. Not only the Investigational Product (IP), but also other medical devices used in the study, e.g. implants, conometric temporization cap and other prosthetic parts should be included in the ADE reporting.

Examples of AEs are e.g. cold, headache and abutment loss at non-study positions.

*Examples of ADEs* are e.g. implant loss, implant fracture, abutment loss, abutment fracture, screw fracture, loss of retention, at study position.

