### 6.4.3 SAE and SADE reporting

SAEs and SADEs must be reported to Dentsply Sirona Implants as soon as the Investigator becomes aware of it.

Dentsply Sirona Implants and the Investigators will distinguish between SAEs related to the medical device and those related to the procedures (any procedure specific to the clinical investigation). An SAE can be related both to procedures and the Investigational Product (IP).

For SAEs and SADEs the Investigator must:

- Record SAE/SADE details in the eCRF immediately, but no later than the end of the next business day (counting from when the Investigator becomes aware of the SAE/SADE), an e-mail will automatically be sent to Dentsply Sirona Implants.
- Follow up the initial SAE/SADE information as soon as new information is available.
- Report to the IEC/IRB any SAEs/SADEs, as per local requirements (in multicentre investigations this may include the SAEs/SADEs reported from another site, this information will be provided by Dentsply Sirona Implants, if required).
- Report to Regulatory Authorities any SAEs/SADEs, as per local requirements (in multicentre investigations this may include the SAEs/SADEs reported from another site, this information will be provided by Dentsply Sirona Implants, if required).
- Provide Dentsply Sirona Implants with all SAE/SADE related documentation and correspondence to the IEC/IRB and/or Regulatory Authority.

A copy of the SAE/SADE Report and associated documents must be filed in the ISF by the Investigator.

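### Sections 6.4.1.2 and 6.4.2 define an ADE differently, so whether a purely procedure-related event counts as a device effect depends on which section is followed

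*Combined protocol and SAP*

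**What the plan says.** Three places in the protocol say what makes an AE an ADE.

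- **6.4.1.2 (definition):** "An ADE is an AE related to the use of the medical device". The section extends this to every medical device used in the study, implants and temporary caps included, and adds: "This includes AEs resulting from insufficient or inadequate instructions for use, installation, or operation, or any malfunction of the medical device". Use error and misuse are also covered. A procedure as a cause in its own right is not mentioned.
- **6.4.2 (reporting rule):** "If an AE is assessed to be device/procedure related it is defined as an ADE". Among the information to be collected is one item: "Medical device/procedure related yes/no".
- **6.4.1.1 (general AE text):** an AE may be reclassified as "ADE, SAE or SADE depending of the severity of the complication, or if judged as related to the medical device or procedure". This leans towards 6.4.2.

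Two further sections depend on the answer. Section 6.4.1.4 builds the serious category on the ADE: "An SADE is an ADE that has resulted in any of the consequences characteristic of a SAE". Section 6.4.3 says that the sponsor and investigators "will distinguish between SAEs related to the medical device and those related to the procedures (any procedure specific to the clinical investigation"), and that one SAE may be related to both. No matching requirement is stated for non-serious events.

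Counts of AEs and ADEs by visit form the only safety outcome (2.3). Section 10.2 splits safety events by whether they began before or after the permanent restoration, and 10.3.3 plans descriptive summaries without tests.

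**The concern.** Both definitions are current text, and they do not describe the same set of events. An investigator or analyst who follows 6.4.2 will count as a device effect an event caused only by a procedure. One who follows 6.4.1.2 will not, but then cannot obtain the ADE count from the combined item, because a yes may mean device, procedure or both.

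This matters because the study is a single-arm post-market follow-up of a new retention mode. No control group shows the background of procedural events, and the value of an ADE count lies in attribution to the device. About nine sites are expected, and sites reading different sections could classify the same event differently.

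**Working it through.** The plan gives no figure to reproduce, and no rate or sample size enters. The check is a comparison of the rules.

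**Step 1. Apply each rule to every combination of causes.** Here 'device' has the broad meaning of 6.4.1.2: any study device, including its installation, operation and use error.

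| Device-related | Procedure-related | Combined item (6.4.2) | ADE under 6.4.1.2 | ADE under 6.4.2 |
|---|---|---|---|---|
| no | no | no | no | no |
| no | yes | yes | **no** | **yes** |
| yes | no | yes | yes | yes |
| yes | yes | yes | yes | yes |

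The rules part in one row, procedure only. It follows that

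ADE count under 6.4.2 − ADE count under 6.4.1.2 = number of purely procedure-related AEs.

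The difference cannot be negative, so 6.4.2 can only give an equal or larger count. The combined item returns the same yes for three of the four rows. These are counts of logical patterns, not of events.

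**Step 2. See whether the examples in 6.4.2 settle it.** The ADE examples are "implant loss, implant fracture, abutment loss, abutment fracture, screw fracture, loss of retention, at study position": six, each a failure or loss of a study device or its retention, so all six qualify under both rules. The three AE examples are a cold, a headache and abutment loss away from the study position. None of the 6 + 3 = 9 examples is presented as purely procedure-related, so they do not show which rule was intended.

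**Step 3. Ask whether the disputed row can occur.** Section 5.1.2 allows minor bone grafting and soft tissue grafting, and 6.1 provides for sedation or general anesthesia. An event caused by one of these need not involve a study device. Whether it counts as procedure-related is less clear. Section 6.4.2 does not define the word, and the only explanation, in 6.4.3, limits it to procedures specific to the investigation. Sedation follows the site's usual practice and grafting is done when needed, so on that meaning both may fall outside and be ADEs under neither rule. The disputed row is therefore possible but narrow, and its edge is undefined.

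**Step 4. Follow the effect to serious events.** Under 6.4.2 with 6.4.1.4, a purely procedure-related SAE becomes a SADE; under 6.4.1.2 it stays an SAE. Section 6.4.3 sets the same reporting steps for both, so only the label and the SADE count change.

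**Step 5. Ask whether the period split in 10.2 resolves it.** Only in part. Surgery precedes the permanent restoration, so purely procedural events should fall mainly in the first period (an inference). But implants, and in some subjects conometric abutments with temporary or healing caps, are also in place then (5.1.2), so that period mixes both causes.

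**The case against.** The strongest reply is that 6.4.2 is the operating rule. It is the reporting section, 6.4.1.1 agrees with it, and 6.4.1.2 omits procedures without expressly excluding them. A site has one item and one rule, so a count can be produced, and any error is towards over-reporting device effects. This shows that the study can run. It does not remove the conflict, because 6.4.1.2 is the section that defines the term, and a count produced under 6.4.2 would be read with that meaning.

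The next reply is that little is at stake. Much of this stands:

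- Installation and use of all study devices are already inside 6.4.1.2, so few events may be in dispute.
- Abutment fracture, abutment loss and loss of retention are components of the primary outcome; implant loss is a secondary outcome; device deficiencies are recorded separately (6.4.4).
- Safety analysis is descriptive, and all subject data will be listed (10.2).

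A reader might also infer that device and procedure causes cannot be separated at all for non-serious events. The documents do not support that. The list in 6.4.2 is introduced as what is included and need not be complete. Event description and action taken are also collected, so a case-by-case review could separate some events, although none is planned. The eCRF is not among the documents, and the content of the Appendix D overview is not legible in the available text. What can be said is narrower: the items listed do not by themselves make the separation. An additional eCRF field would cure that, but would leave the two definitions in conflict.

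**Conclusion.** The point holds as a contradiction between two definitions, limited to purely procedure-related AEs. For these, the ADE count in 2.3 and the SADE label depend on the section followed. That the wording differs is certain; that the data cannot be separated from the listed items is conditional on the eCRF holding no further field.

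The number of affected events cannot be estimated, since no event rates are given, and is probably small. A reader might take one pattern in four, or three in four, as the share of events misclassified, or infer that the ADE count is heavily inflated. Neither follows, because the patterns are not equally frequent and their frequencies are unknown. Nor does the conflict weaken the reporting of serious events, which takes the same route under either label. Total AE and SAE counts, the primary outcome, its test and the sample size are unaffected. The plan should be corrected because the conflict sits in its only safety outcome and is inexpensive to remove.

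**What to change.** 1. Use one ADE definition in 6.4.1.1, 6.4.1.2 and 6.4.2, taking the device-based text of 6.4.1.2. The SADE in 6.4.1.4 then follows without further change.
2. For all AEs, replace the combined item with two yes/no items, device related and procedure related, both of which may be yes. State in 6.4.2 that procedure has the meaning given in 6.4.3.
3. In 10.3.3, report ADEs and procedure-related AEs separately, within the two periods of 10.2.

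The cost is one extra eCRF item per AE and a protocol amendment, which may need ethics committee notification or approval under 7.1. No visit or procedure is added. Returning to source records for AEs already entered is not needed to resolve the contradiction; events that carry only the combined answer can be shown under the wider label described next.

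If the item cannot be changed, align 6.4.1.2 to 6.4.2 and label the reported count as device- or procedure-related, so that it is not read as a count of device effects. This needs wording edits and the amendment only, but leaves the two causes unseparated for non-serious events.

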### 6.4.3 SAE and SADE reporting

SAEs and SADEs must be reported to Dentsply Sirona Implants as soon as the Investigator becomes aware of it.

Dentsply Sirona Implants and the Investigators will distinguish between SAEs related to the medical device and those related to the procedures (any procedure specific to the clinical investigation). An SAE can be related both to procedures and the Investigational Product (IP).

For SAEs and SADEs the Investigator must:

- Record SAE/SADE details in the eCRF immediately, but no later than the end of the next business day (counting from when the Investigator becomes aware of the SAE/SADE), an e-mail will automatically be sent to Dentsply Sirona Implants.
- Follow up the initial SAE/SADE information as soon as new information is available.
- Report to the IEC/IRB any SAEs/SADEs, as per local requirements (in multicentre investigations this may include the SAEs/SADEs reported from another site, this information will be provided by Dentsply Sirona Implants, if required).
- Report to Regulatory Authorities any SAEs/SADEs, as per local requirements (in multicentre investigations this may include the SAEs/SADEs reported from another site, this information will be provided by Dentsply Sirona Implants, if required).
- Provide Dentsply Sirona Implants with all SAE/SADE related documentation and correspondence to the IEC/IRB and/or Regulatory Authority.

A copy of the SAE/SADE Report and associated documents must be filed in the ISF by the Investigator.

